We aim to invite a minimum of 40 participants to the Stakeholder Workshop.

Page 19 of 28 Midwifery Units Study – Protocol/FINAL V1 / 25 February 2016

Total anticipated number of participants 286.

ADVERSE EVENTS

The occurrence of an adverse event as a result of participation within this study is not expected and no adverse event data will be collected.

ETHICAL AND REGULATORY ASPECTS

Participation will be voluntary and participants will choose what they wish to disclose. We do not anticipate that participation in the focus groups, interviews or workshop will cause distress to participants; however should that occur, participating NHS Staff will be advised to seek support from their supervisor and service users will be advised to contact the Patient Advice and Liaison Service or a member of their clinical care team. We will minimise inconvenience and demands on participants and offer flexibility to support participation; for example focus groups and interviews will be conducted within participants local area.

It is highly unlikely participants will disclose any information that is deemed to be a criminal offence or require further action. If information is disclosed that could pose a risk of harm to the participant or others, the research team will discuss it and report accordingly where appropriate. If information is disclosed during focus groups or interviews that relates to poor practice, the research fellows will discuss it with the Chief Investigator and, where appropriate, report accordingly to the Manager of the relevant Trust.

Where research staff may undertake interviews and site visits alone, the University of Nottingham Lone Working Policy will be adhered to.

ETHICS COMMITTEE AND REGULATORY APPROVALS

Phase 1 of the study is a service evaluation and therefore does not require ethical review.

Phase 2 and 3 of the study will not be initiated before the protocol, consent forms and participant information sheets have received approval / favourable opinion from the Research Ethics Committee (REC), and the respective National Health Service (NHS) Research & Development (R&D) department. Should a protocol amendment be made that requires REC approval, the changes in the protocol will not be instituted until the amendment and revised informed consent forms and participant information sheets have been reviewed and received approval / favourable opinion from the REC and R&D departments. A protocol amendment intended to eliminate an apparent immediate hazard to participants may be implemented immediately providing that the REC are notified as soon as possible and an approval is requested. Minor protocol amendments only for logistical or administrative changes may be implemented immediately; and the REC will be informed.

The study will be conducted in accordance with the ethical principles that have their origin in the Declaration of Helsinki (1996); the principles of Good Clinical Practice, and the Department of Health Research Governance Framework for Health and Social care (2005).

INFORMED CONSENT AND PARTICIPANT INFORMATION

The process for obtaining participant informed consent will be in accordance with the REC guidance, and Good Clinical Practice (GCP) and any other regulatory requirements that might be introduced. The investigator or their nominee and the participant shall both sign and date the Consent Form before the person can participate in the study. The participant will receive a copy of the signed and dated forms.

Page 20 of 28 Midwifery Units Study – Protocol/FINAL V1 / 25 February 2016

The decision regarding participation in the study is entirely voluntary. The investigator or their nominee shall emphasize to them that consent regarding study participation may be withdrawn at any time without penalty or affecting the quality or quantity of their future medical care, or loss of benefits to which the participant is otherwise entitled. No study-specific interventions will be done before informed consent has been obtained.

The investigator will inform the participant of any relevant information that becomes available during the course of the study, and will discuss with them, whether they wish to continue with the study. If applicable they will be asked to sign revised consent forms.

If the Consent Form is amended during the study, the investigator shall follow all applicable regulatory requirements pertaining to approval of the amended Consent Form by the REC and use of the amended form (including for ongoing participants).

RECORDS

All participants will be made aware that all data will be anonymised with pseudonyms applied.

Each participant will be assigned a study identity code number, for use on transcripts, other study documents and the electronic database. The documents and database will also use their initials (of first and last names separated by a hyphen, or a middle name initial when available).

Transcripts and other study documents and databases, will be treated as confidential documents and held securely in accordance with regulations. Transcripts and other study documents and database shall be restricted to those personnel approved by the Chief or local Investigator and recorded as such in the study records.

All paper forms shall be filled in using black ballpoint pen. Errors shall be lined out but not obliterated by using correction fluid and the correction inserted, initialled and dated. The Chief or local Investigator shall sign a declaration ensuring accuracy of data recorded in the transcriptions or other study data.

Source documents

Source documents shall be filed at the investigator's site and may include but are not limited to, consent forms, study records, field notes, interview transcriptions and audio records. Only study staff shall have access to study documentation other than the regulatory requirements listed below.

Direct access to source data / documents

All source documents shall made be available at all times for review by the Chief Investigator, Sponsor's designee and inspection by relevant regulatory authorities.

DATA PROTECTION

All study staff and investigators will endeavour to protect the rights of the study's participants to privacy and informed consent, and will adhere to the Data Protection Act, 1998. The researchers will only collect the minimum required information for the purposes of the study and this information will be held securely, in a locked room, or locked cupboard or cabinet. Access to the information will be limited to the study staff and investigators and any relevant

Page 21 of 28 Midwifery Units Study – Protocol/FINAL V1 / 25 February 2016

regulatory authorities (see above). Computer held data including the study database will be held securely and password protected. All data will be stored on a secure dedicated web server. Access will be restricted by user identifiers and passwords (encrypted using a one way encryption method).

Electronic data will be backed up every 24 hours to both local and remote media in encrypted format.

QUALITY ASSURANCE & AUDIT

INSURANCE AND INDEMNITY

Insurance and indemnity for clinical study participants and study staff is covered within the NHS Indemnity Arrangements for clinical negligence claims in the NHS, issued under cover of HSG (96)48. There are no special compensation arrangements, but study participants may have recourse through the NHS complaints procedures.

The University of Nottingham as research Sponsor indemnifies its staff, research participants and research protocols with both public liability insurance and clinical trials insurance. These policies include provision for indemnity in the event of a successful litigious claim for proven non-negligent harm.

STUDY CONDUCT

Study conduct may be subject to systems audit for inclusion of essential documents; permissions to conduct the study; CVs of study staff and training received; local document control procedures; consent procedures and recruitment logs; adherence to procedures defined in the protocol (e.g. inclusion / exclusion criteria); accountability of study materials.

STUDY DATA .

Monitoring of study data shall include confirmation of informed consent; source data verification; data storage and data transfer procedures; local quality control checks and procedures, back-up and disaster recovery of any local databases and validation of data manipulation. The Study Coordinator, or where required, a nominated designee of the Sponsor, shall carry out monitoring of study data as an ongoing activity.

Study data and evidence of monitoring and systems audits will be made available for inspection by the REC as required.

RECORD RETENTION AND ARCHIVING

In compliance with the University of Nottingham Code of Research Conduct and Research Ethics, the Chief or local Principal Investigator will maintain all records and documents regarding the conduct of the study. These will be retained for at least 7 years or for longer if required. If the responsible investigator is no longer able to maintain the study records, a second person will be nominated to take over this responsibility.

The study documents held by the Chief Investigator on behalf of the Sponsor shall be finally archived at secure archive facilities at the University of Nottingham. This archive shall include all anonymised audio recordings, study databases and associated meta-data encryption codes.

Page 22 of 28 Midwifery Units Study – Protocol/FINAL V1 / 25 February 2016

DISCONTINUATION OF THE STUDY BY THE SPONSOR

The Sponsor reserves the right to discontinue this study at any time for failure to meet expected enrolment goals, for safety or any other administrative reasons. The Sponsor shall take advice as appropriate in making this decision.

STATEMENT OF CONFIDENTIALITY

Individual participant medical (for service users) or personal information obtained as a result of this study are considered confidential and disclosure to third parties is prohibited with the exceptions noted above.

Participant confidentiality will be further ensured by utilising pseudonyms.

If information is disclosed during the study that could pose a risk of harm to the participant or others, the researcher will discuss this with the CI and where appropriate report accordingly.

Data generated as a result of this study will be available for inspection on request by University of Nottingham representatives, the REC, local R&D Departments and the regulatory authorities.

PUBLICATION AND DISSEMINATION POLICY

Following approval of workshop outcomes by the funder, the interventions and service guidance that have been developed from the workshop will be made available to commissioners and providers of maternity services in England. The guidance will address both services currently without MUs to facilitate the establishment of MUs and services that need to maximise utilisation of existing MUs. The guidance will be disseminated via email and post to commissioner and provider groups across England, through the existing maternity and neonatal networks, whose representatives have participated in the stakeholder workshop. In addition, they will also be sent to the NICE Intrapartum Guideline Group, the Royal College of Midwives Heads of Midwifery network in England, the Department of Health, the all-party parliamentary group on Maternity and all other organisations and professional bodies represented by the workshop stakeholders.

A final and full research report detailing all the work undertaken, an abstract and an executive summary will be made available on the HSDR programme website. PowerPoint slides (up to 10 maximum) which present the main findings will be made available on the HDSR programme website.

All participants in the research will be sent an Executive Summary of the findings (a plain English summary in accessible language will be produced for service-users). The plain English summary will be reviewed by the study PPI representatives, before distribution.

In addition to the research being published in the NIHR HS&DR Journal, key themes within the findings and interventions/service guidance will be published in high impact journals targeting midwifery, obstetric, sociology of organisations and sociology of health/reproductive studies, particularly those with Open Access. In addition, papers will be submitted to nonacademic professional journals like MIDIRS. As the user organisations (NCT, AIMS, National Federation of Women's Institutes, Mumsnet, BirthChoiceUK) are either on our Advisory Group or involved in the stakeholder workshop, we will offer summaries for their respective journals and web sites.

The key findings, implications, proposed interventions and service guidance will be presented by the CI and members of the research team at a range of international and

Page 23 of 28 Midwifery Units Study – Protocol/FINAL V1 / 25 February 2016

national conferences: NHS Confederation Conference, NICE Annual Conference, International Confederation of Midwives' Congress, British Perinatal Medicine Society. All impact activities will be supported by a project webpage, a regular project newsletter and Twitter account.

BirthChoiceUK will release a press statement on the primary findings.

Participants will not be identified in any publications.

USER AND PUBLIC INVOLVEMENT

Service users (from both local and national groups) have been involved at all stages of the development of the study and are represented in its advisory, and management groups. An experienced service user representative is a co-applicant on the bid.

Members of the Nottingham Maternity Research Network will review our draft posters, information leaflets, consent forms and data collection tools. In addition, they will provide advice from the patient perspective, throughout the life time of the project, comment on design of information materials for women, focus group and interview schedules and review the interpretation of findings, the proposed interventions and service guidance.

Service users will be reimbursed for all out of pocket expenditure, and receive acknowledgement for their contribution, according to INVOLVE guidelines. Members of the Nottingham Maternity Research Network will also be invited to take part contribute in the stakeholder workshop.

We are asking a member(s) of the Nottingham Maternity Research Network to co-facilitate the user focus groups in the 6 case study sites. Training will be provided and all appropriate clearances will be obtained appropriate to the co-researcher role.

STUDY FINANCES

Funding source

This study is funded by NIHR Health Services and Delivery Research Programme

Participant stipends and payments

Participants will not be paid to participate in the study. Reimbursement of travel and childcare expenses will be offered to service-users for expenses incurred during focus group/interview attendance. Additionally, a high-street voucher of £10 will be provided to service-users upon completion of a focus group. Travel expenses will be reimbursed to stakeholders who attend a workshop.

Page 24 of 28 Midwifery Units Study – Protocol/FINAL V1 / 25 February 2016

SIGNATURE PAGES

Signatories to Protocol:

Chief Investigator: (name)_____

Signature:_____

Date: _____

Page 25 of 28 Midwifery Units Study – Protocol/FINAL V1 / 25 February 2016

REFERENCES

Anim-Somuah, Smyth R, Howell C Epidural versus non-epidural or no analgesia in labour. The Cochrane Database of Systematic Reviews 2009, Issue 1.

Anderson R A & Crabtree B F (2005) Case study research: The view from complexity science. Qualitative Health Research 15(5): 669-685.

Bertrand I & Hughes P (2005) Media Research Methods. Audiences, Institutions, Texts. London, Palgrave Macmillan.

Bourke, N (2013) Support overdue: women's experience of the maternity service. London: NFWI.

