Methods of analysis	Descriptive statistics and narrative description of configuration, organisation and operation of AMUs and FMUs. Content and thematic analysis of local media coverage, focus group discussions and individual interviews. Synthesis of information generated at the workshop to develop a final set of proposed interventions and recommendations.

Page 5 of 28 Midwifery Units Study – Protocol/FINAL V1 / 25 February 2016

ABBREVIATIONS

- AMU Alongside Midwifery Unit
- CI Chief Investigator overall
- FMU Free-standing Midwifery Unit
- GCP Good Clinical Practice
- HoM Head of Midwifery
- MU Midwifery-led Unit
- NHS National Health Service
- OU Obstetric-led Unit
- PALS Patient Advice and Liaison Service
- PI Principal Investigator at a local centre
- PIS Participant Information Sheet
- R&D Research and Development Department
- REC Research Ethics Committee
- UoN University of Nottingham

Page 6 of 28 Midwifery Units Study – Protocol/FINAL V1 / 25 February 2016

TABLE OF CONTENTS

SYNOPSIS	4
ABBREVIATIONS	6
STUDY BACKGROUND INFORMATION AND RATIONALE	9
STUDY OBJECTIVES AND PURPOSE	10
PURPOSE OBJECTIVES	10 10
STUDY DESIGN	11
STUDY CONFIGURATION STUDY MANAGEMENT DURATION OF THE STUDY AND PARTICIPANT INVOLVEMENT End of the Study SELECTION AND WITHDRAWAL OF PARTICIPANTS Recruitment Eligibility criteria Inclusion criteria Exclusion criteria Expected duration of participant participation Participant Withdrawal Informed consent STUDY REGIMEN Compliance Criteria for terminating the study	11 11 12 12 12 12 14 14 15 15 15 15 15 16 19 19
ANALYSES	19
Methods Sample size and justification	19 19
ADVERSE EVENTS	20
ETHICAL AND REGULATORY ASPECTS	20
ETHICS COMMITTEE AND REGULATORY APPROVALS INFORMED CONSENT AND PARTICIPANT INFORMATION RECORDS Source documents Direct access to source data / documents DATA PROTECTION	20 20 21 21 21 21 21
QUALITY ASSURANCE & AUDIT	22
INSURANCE AND INDEMNITY STUDY CONDUCT STUDY DATA . RECORD RETENTION AND ARCHIVING DISCONTINUATION OF THE STUDY BY THE SPONSOR STATEMENT OF CONFIDENTIALITY	22 22 22 22 22 23 23 23
PUBLICATION AND DISSEMINATION POLICY	23
Page 7 of 28 Midwifery Units Study – Protocol/FINAL V1 / 25 February 2016	

USER AND PUBLIC INVOLVEMENT	24
STUDY FINANCES	24
Funding source Participant stipends and payments	24 24
SIGNATURE PAGES	25
REFERENCES	

Page 8 of 28 Midwifery Units Study – Protocol/FINAL V1 / 25 February 2016

STUDY BACKGROUND INFORMATION AND RATIONALE

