Prior research on broader organisational change in the NHS described multifaceted barriers and drivers to change (Iles and Sutherland, 2001; Greenhalgh et al, 2004). Considering this work, a wide range of factors may facilitate or create barriers to the establishment and utilisation of MUs, including issues of staffing, service leadership, attitudes and preferences of childbearing women and staff, the influence of local media's reporting of changes in local maternity services, perceptions of clinical risk e.g. safety of FMUs regarding the absence of medical backup on site and need for ambulance transfer if labour complications develop (McCourt et al, 2012; Bourke, 2013) and finally, the relationship between professional groups. Currently, the prevalence and impact of such potential barriers remain unclear. This is important to know so potential interventions and service guidance can be developed to address barriers and facilitators of MUs and then utilised for future maternity services commissioning and provision.

Our study will explore the reasons for the variable provision of MUs in England by undertaking comparative case studies in the high achieving (those birthing 20% of more of low risk women in MUs) and low achieving services (those birthing 10% or less in MUs) and will then identify interventions to address barriers and facilitators of MUs. This work will inform a national maternity care stakeholder workshop near the end of the project which aims to identify potential interventions to address barriers and facilitators of MUs for maternity care commissioners and providers.

In summary, there are substantial benefits to be realised for childbearing women and for the NHS if low risk women across England deliver in MUs. We want to investigate why some services have 20% or more of their population of pregnant women birthing in these facilities while others, either have no MUs or 10% or less of their women using them. With the results, we will identify interventions to address barriers and facilitators of MUs and develop service guidance to inform future maternity service commissioning and provision.

STUDY OBJECTIVES AND PURPOSE

PURPOSE

The purpose of the research is to investigate the barriers and facilitators to provision of MUs across England, to identify interventions to increase MU provision and uptake and to develop service guidance based on these for commissioners and providers.

OBJECTIVES

Phase 1 Objectives:

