Should there be any subsequent amendment to the final protocol, which might affect a participant's participation in the study, continuing consent will be obtained using an amended Consent Form which will be signed by the participant.

STUDY REGIMEN

Phase 1 – Service Evaluation

Mapping of the configuration, organisation and operation of MUs in England. Service evaluation element not included in this protocol.

Phase 2 - Selection of case study sites:

Using the data from Phase one, six case study sites will be purposively sampled:

- 2 higher performing services with both an AMU and a FMU achieving 20% or more of total births
- 2 lower performing services with one or more MUs (AMU and/or FMU) achieving 10% or less of total births
- 2 services with no MUs

Within each of the three categories, study sites will be chosen to represent both rural and urban settings to enhance representativeness, if possible. One case study site is planned to be in London.

Data collection at each case study site:

Research Fellows will undertake data collection at each of the six sites, including;

Semi-structured Interviews:

Chief Executive of Hospital Trust, Head of Midwifery, senior obstetrician, midwifery management lead for community, business manager of maternity service, neonatologist, MSLC service user or service-user group representative, local maternity support/campaigning groups. In addition, snowball sampling will be used to identify other key individuals that have shaped the local development of maternity services.

Questions will be focused on discussing the evolution of services in each of the sites. Interview schedules will be developed by the research team, drawing on the findings from the first stage of the study, existing literature regarding the organisation of maternity services, literature on implementation and organisational change, as well as the expertise of the project's service user reference group and project advisory group and piloted prior to use.

Participants will be invited to one audio recorded semi-structured interview. Interviews will be undertaken within one of the six NHS Trusts, or over the telephone. The interview will be conducted by one Research Fellow. A topic guide/interview questionnaire will be developed, informed by literature and the service evaluation stage of the study. Questions will be focussed on the evolution of services in the host site.

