A topic guide will be developed, informed by literature and the service evaluation stage of the study. Questions will be posed to explore such issues as choice of birth place and barriers and facilitators for MU use.

Focus groups will be audio recorded and professionally transcribed verbatim. Pseudonyms will be applied to all interviewees and any site identifying data will be anonymised.

GP Locality Lead telephone interviews:

At least one commissioning GP Locality Lead proximal to each case study site, will be invited to a telephone interview. Each Locality lead GP will be asked questions about the barriers and facilitators for the utilisation of MUs.

Documentary analysis:

Review of policies, protocols, guidelines and minutes of strategic meetings related to birth place choices/provision in each of the sites.

Local media analysis (radio, TV, newspapers) of stories about local maternity services:

In case study sites where researchers are notified of relevant media outputs (local newspapers, TV, radio), debates and discussions within these outputs will be explored and the presentation of local maternity provision will be examined. This will enable the team to Page 17 of 28

Midwifery Units Study – Protocol/FINAL V1 / 25 February 2016

further understand the local context and potential influences on local demand and service provision.

Phase 3 -

After barriers and facilitators have been reviewed by the entire team, we will then develop potential interventions and service guidance that will subsequently be discussed with the service user reference group, members of the advisory and stakeholder groups. The exact nature of the interventions that we will develop cannot be specified prior to data collection. They are likely to be multifaceted or complex interventions of behavioural, organizational and/or policy change, rather than discrete technical or clinical interventions (Craig et al 2008).

Findings from phase 1 and 2 will allow us to identify potential interventions, and draw out the theory of change (the cause and effect model) by which these interventions are understood to work (Weiss, 1998). In developing potential interventions, existing evidence from other studies will also be reviewed to identify the forms of interventions that have previously been used to address the type of barriers we identify. In addition to this, a stakeholder workshop (details provided below) will be held to allow detailed discussion of the potential interventions.

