Reimbursement of travel expenses for workshop attendance will be offered to all participants.

Compliance

This is not a treatment study, therefore issues of compliance are not applicable.

Criteria for terminating the study

We do not envisage circumstances that would require early termination of the study. The study as a whole will end after the Stakeholder Workshop and completion of data synthesis.

ANALYSES

Methods

Phase 1 – Service Evaluation element

Not included in this protocol

Phase 2 - Focus group discussions, interview data and Local media analysis.

Focus group discussions and interview data will be fully transcribed, and thematic analysis will be undertaken, with transcripts being read and re-read to identify relevant themes (Braun & Clarke, 2006). Analysis will begin as data is collected and will be utilised to inform later focus groups. NVivo software will be used to assist with the thematic analysis of interviews/focus groups.

Local media output will be analysed thematically using insights from critical discourse analysis, to ascertain both extent of local debate and the ways in which key issues have been framed (Machin & Meyer 2010). This will add to an understanding of the broader context of service provision and this analysis will be integrated into the case comparison in phase three of the project.

Phase 3 - Stakeholder Workshop

The research team will synthesise information generated at the workshop to develop a final set of proposed interventions and recommendations and content for commissioning guidance for inclusion in the final report.

All analysis will be undertaken on University of Nottingham computers and backed-up to the University of Nottingham secure servers.

Sample size and justification

This is an exploratory study; therefore no formal estimates of sample size have been undertaken. However 4 focus groups will be conducted in each of the 6 participating NHS Trusts, in order to represent a range of local contexts and birth place options. We plan to include up to 8 participants per group, providing a maximum of 192 participants. In addition to the focus groups, staff and service-user representative interviews will be conducted at each of the six NHS Trusts. Approximately nine staff/service-user representative interviews will be conducted at each trust, totalling 54 interviews. The sample size of each focus group and number of interviews conducted, may vary in accordance with participant availability and withdrawals.

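### Collecting local media only where researchers are notified of it does not support the aim of establishing the extent of local debate

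*Protocol*

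**What the plan says.** Under Study Regimen, Local media analysis, the protocol sets the condition for collection: "In case study sites where researchers are notified of relevant media outputs". Where it is met, the researchers will look at the debates in that output and at how local maternity provision is presented. The stated purpose is to understand local context and possible influences on demand and provision.

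Under Analyses, Methods, Phase 2, the same material is to be analysed thematically, drawing on critical discourse analysis, "to ascertain both extent of local debate and the ways in which key issues have been framed". The section adds that "this analysis will be integrated into the case comparison in phase three of the project".

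Three other places bear on the point:

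- Study Regimen, Data collection at each case study site, opens with "Research Fellows will undertake data collection at each of the six sites, including". The media analysis is among the components that follow.
- The Synopsis, Methods of analysis, promises "Content and thematic analysis of local media coverage, focus group discussions and individual interviews", with no condition on notification.
- Study Background Information and Rationale names "the influence of local media's reporting of changes in local maternity services" among the factors that may help or hinder midwifery units.

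**The concern.** Extent is a statement about quantity: how much debate there was at a site. To establish it, and to set one site beside another, the material must be looked for in a comparable way at each site. The protocol instead lets material in when someone brings it to the researchers' attention, and leaves that route undefined.

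At stake is one named explanatory factor. The design has six sites, two in each of three categories: high use of midwifery units, low use, and no unit. With two sites per category, one site without notified items leaves half of that category's media evidence missing. If the gap is read as little or no debate, an ascertainment difference could be mistaken for a difference between services. The barriers identified then feed the interventions and service guidance of Phase 3.

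**Working it through.** The plan gives no figure on this point and there is none to reproduce. The check is a comparison of what the protocol says in each place, with one line of structure.

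**Step 1: collection rule against analysis aim.**

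| Element | Where in the protocol | What it fixes |
|---|---|---|
| Entry of media items | Study Regimen, Local media analysis | Only at sites where researchers are notified |
| Aim | Analyses, Methods, Phase 2 | Extent of debate, and framing |
| Use | Analyses, Methods, Phase 2 | Integrated into the case comparison |
| Coverage of sites | Study Regimen, Data collection at each case study site | All six sites |
| Summary of method | Synopsis | Local media coverage, without condition |

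The first row is conditional on an event outside the researchers' stated control. The fourth and fifth carry no such condition. The documentary analysis, described just before the media analysis, is to be done at every site, so the condition is particular to media.

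**Step 2: is a search supplied elsewhere?** No. The protocol lists no outlets, terms, time window or inclusion rule for media items, and does not identify the notifiers.

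**Step 3: what the rule lets the study observe.** For site *i*, let *N_i* be the true number of relevant items and *p_i* the probability that an item is notified. The expected number seen is

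*n_i = N_i × p_i*.

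For two sites *a* and *b*,

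*n_a / n_b = (N_a / N_b) × (p_a / p_b)*.

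The protocol gives no information on any *p_i*. Three consequences follow:

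- If *p_a = p_b*, the second factor is 1 and relative extent is preserved, though absolute extent is still unknown.
- If they differ, observed relative extent is distorted by *p_a / p_b*. That ratio may lie above or below 1, so neither direction nor size can be given.
- *n_i = 0* arises when *N_i = 0* and also when *p_i = 0*. The media strand alone cannot separate these.

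The formula is only a way to make the reasoning explicit. The same holds if extent is judged qualitatively, because the judgement still rests on the items that were seen.

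**Step 4: framing.** Notified items can be read for how they frame the issues whatever *p_i* is. Which items are read still depends on the notifier, so framing is less affected than extent, but not immune.

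**The case against.** The strongest reply is that this is a qualitative, contextual strand of an exploratory study. The protocol says so in general terms: "This is an exploratory study; therefore no formal estimates of sample size have been undertaken". The method is thematic, no count of items is planned, and no contrast in volume between the three site categories is specified. No Phase 2 objective names the media. Being notified also does not exclude an orderly arrangement, such as asking contacts at every site the same question.

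Much of this stands, and it limits the point. A reader might infer that the comparison *is* biased, for instance that sites with active campaigns will appear to have more debate. The documents do not support that: they do not say who notifies, so bias is possible but not shown.

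A reader might also infer that sites without notified items fall out of the case comparison. They do not. Each site still has four planned focus groups, about nine interviews (including service-user representatives and local campaigning groups), an invited GP locality lead and a review of documents. Such a site lacks only the media strand. Those sources may reveal some coverage, but the protocol does not commit any of them to asking about media, so they do not close the gap.

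The reply does not rescue the word extent. Opportunistic material can support an account of framing. A finding on extent that enters a comparison of cases needs comparable ascertainment, whether or not anything is counted. Nor is this a detail that could be left to an analysis plan, since the protocol itself fixes both the collection rule and the aim.

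**Conclusion.** The concern holds as a mismatch within the protocol. The rule for collecting media items does not support the aim of ascertaining the extent of local debate and taking it into the case comparison. It also sits badly with data collection at each of the six sites and with the unconditional wording of the Synopsis.

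Extent is open to uncontrolled ascertainment bias of unknown direction and size. This conclusion rests on two readings: that the notification route is unspecified and may differ between sites, and that no search is stated elsewhere in the protocol. If one uniform route were in fact used at all six sites, the risk to relative extent would be smaller, but the protocol would still need to say so.

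The importance is moderate: media reporting is one of several candidate factors and one strand among several sources.

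**What to change.** Make one of two changes.

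(a) **Keep extent and collect for it.** Apply the same search at all six sites: a list of local outlets for each Trust area, the same terms and the same date window. Record a search that finds nothing as a result in its own right. Keep notified items as a flagged supplement, used for framing only. The cost is some research-fellow time, for which the protocol gives no hours or budget, and thinner archive coverage of radio and television than of print and online news. That limitation should be reported.

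(b) **Drop extent.** Delete that aim and any cross-site comparison of extent, and limit the strand to the framing of the items obtained. State that the absence of notified items is not evidence of the absence of coverage. This costs only wording.

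Under either option, align the Synopsis, Study Regimen and Analyses sections so that they describe the same collection rule. The change is easiest before the site work of Phase 2, with enrolment planned for months 7 to 16.
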